7.1 Sample Size Determination

Power analysis was performed using preliminary data from a study using ¹¹C-PBR28 PET in patients with AD and MCI and healthy controls.

For the main effects, the minimal detectable effect size is Cohen $d=0.74$ with the sample size $N=30$ per group, 80% of power and a two-sided test at the 5% significance level. Based on my preliminary data using ¹¹C-PBR28, the effect size for the group difference between MCI and controls is $d=1.3$ (hippocampal SUVR mean (SD) of MCI: 0.98 (0.18); HC: 0.82 (0.06)), and it is similar ($d=1.3$) after adjusting for TSPO genotype. Although these preliminary results were not controlled for amyloid, with the assumption of additive effect of amyloid I would be able to

detect the group difference between amyloid-positive MCI and amyloid-positive without impairment with more than enough power. For the interaction between diagnosis and amyloid, if the mean differences between positive/negative amyloid among the subjects with and without impairment differ by $d=1.06$, I would be able to detect such effect size with 80% power at 5% significance level for a two-sided test.

We also plan to compare ^{11}C -PBR28 binding with the amount and distribution of binding with ^{18}F -MK-6240, a tau radioligand that will be used under a separate IND (#135,864). Because some subjects who have ^{11}C -PBR28 PET may not wish to also undergo ^{18}F -MK-6240 PET, we need to increase the number of subjects so that a total of 60 subject receive both ^{11}C -PBR28 and ^{18}F -MK-6240 PET.

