3.1.4 Image processing

FreeSurfer (<http://surfer.nmr.mgh.harvard.edu/>), the MRI software package comprising a suite of automated tools for segmentation, reconstruction, and derivation of regional volumes and surface-based rendering, will be used for derivation of regions-of-interest (ROIs). Eleven ROIs will be extracted from the structural T1 image: entorhinal cortex, hippocampus, inferior temporal cortex, combined superior and middle temporal cortex, superior parietal lobule, inferior parietal lobule, precuneus, occipital cortex, prefrontal cortex, striatum, and thalamus. Age-adjusted hippocampal volumes will be used to define the presence or absence of neurodegeneration[28]. A single static ^{18}F -florbetaben image acquired 50-70 or 90-110 min post-injection will be read by a trained investigator blinded to the subject's diagnosis. A visual binary read (positive or negative) will be determined according to criteria established by Piramal imaging to stratify subjects as amyloid-positive or amyloid-negative. Semi-quantitative measurement of ^{18}F -florbetaben binding will be used as an outcome measure for baseline amyloid burden (see below).

^{18}F -Florbetaben and ^{11}C -PBR28 PET images will be analyzed according to previously published methods for ^{11}C -PBR28[19]. In brief, Freesurfer based ROIs will be applied to coregistered PET images. Correction for partial volume effects using a region-based voxel-wise method[48] will be applied. Regional time-activity curves using 50-70 or 90-110 min of scan data for ^{18}F -florbetaben and 60-90 min for ^{11}C -PBR28 will be extracted from the PET scans, including cerebellum which will be used as a reference region. Standardized uptake value ratio (SUVR) values will be calculated by dividing SUV values for each target region by that of the cerebellum.

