7.2 Statistical Methods

Subjects will be stratified using a two factor design based on diagnosis (impaired vs. normal) and amyloid status (positive vs. negative). Target sample size is 25 subjects per group (100 subjects total). ^{11}C -PBR28 binding will be the primary outcome measures. Between-group differences in SUVR values from ^{11}C -PBR28 PET images will be compared in each of the 11 ROIs. Analysis will be performed using a two-way MANCOVA with diagnosis (MCI vs. normal) and amyloid status (positive vs. negative) as independent variables and TSPO genotype status (high affinity vs. mixed affinity binder) as covariate. I will additionally test the interaction between diagnosis and amyloid status. This model will be fitted using PROC GLM in SAS.

Regression models will be fit for ^{11}C -PBR28 binding as dependent variable and cognitive scores, voxel count on MRI, ^{18}F -florbetaben binding, and CSF concentrations of markers of inflammation and neurodegeneration as independent variables.

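### The power figures in Section 7.1 are single-outcome calculations at 30 per group and do not describe the 11-region MANCOVA at 25 per cell named in Section 7.2

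*Combined protocol and SAP*

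**What the plan says.** Section 7.1 makes two power statements. The one on main effects reads: "the minimal detectable effect size is Cohen $d=0.74$ with the sample size $N=30$ per group, 80% of power and a two-sided test". Its significance level is 5%. For the interaction, the amyloid difference among impaired subjects is taken to differ from that among unimpaired subjects by d=1.06, and the investigator states "I would be able to detect such effect size with 80% power at 5% significance level for a two-sided test". The pilot effect quoted in support (d=1.3, MCI against controls) is for hippocampal SUVR only.

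Section 3.1.4 defines the outcomes: "Eleven ROIs will be extracted from the structural T1 image". Section 7.2 sets 25 subjects per group (100 in total) and names the analysis: "Analysis will be performed using a two-way MANCOVA with diagnosis (MCI vs. normal) and amyloid status (positive vs. negative) as independent variables". TSPO genotype is the covariate and the interaction is tested as well. The same section says groups will be compared in each of the 11 regions. It names no primary region and gives no multiplicity rule.

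**The concern.** Each 1-df effect in the planned MANCOVA (diagnosis, amyloid status, interaction) is tested by a multivariate F with 11 numerator degrees of freedom. Its power depends on the 11-by-11 correlation matrix of the regional SUVRs and on how the effect is spread over regions. Section 7.1 mentions no number of outcomes, no correlation, no regional pattern and no multivariate test, so its 80% appears to belong to a different test from the one planned.

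What is at stake is how a negative result is read. If the MANCOVA interaction is not significant, Section 7.1 invites the reader to treat it as a null with 80% power behind it. That support is missing, because power for the planned test could be well below or well above 80%.

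**Working it through.** **Inputs from the documents.** Section 7.1: d=0.74, d=1.06, 30 per group, 80% power, two-sided 5%. Section 7.2: 25 per cell, four cells, one covariate, 11 outcomes. **Assumed, because the documents give no value:** an exchangeable between-region correlation rho, shown from 0.3 to 0.9.

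**Step 1. Reproduce the plan's figures on one outcome.**
- Main effect, 30 against 30: noncentrality 0.74 × sqrt(30/2) = 2.87, 58 df, power 80.5%.
- Interaction, 30 per cell: the contrast of four cell means has standard error sqrt(4/30) in SD units, so noncentrality is 1.06/sqrt(4/30) = 2.90. Power is 80.1% with 29 df and 82.1% with 115 df (4 × 30 − 5).

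Both statements are recovered with one outcome and 30 per group.

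**Step 2. The same interaction test at 25 per cell.** Noncentrality is 1.06/sqrt(4/25) = 2.65 with 95 df, giving 74.6%.

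**Step 3. The 11-outcome test.** For a 1-df hypothesis the multivariate test is an exact F with df1 = 11 and df2 = (4n − 5) − 10, which is 85 at n=25 and 105 at n=30. For the interaction the noncentrality is (n × d²/4) × c, where c = v'R⁻¹v, R is the correlation matrix, and v is 1 in affected regions and 0 elsewhere. The first factor is 25 × 1.1236/4 = 7.02 at 25 per cell and 8.43 at 30. If all regions share the effect, c = 11/(1 + 10 rho).

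| rho | c | 30 per cell | 25 per cell |
|---|---|---|---|
| 0.3 | 2.75 | 90% | 81% |
| 0.5 | 1.83 | 71% | 60% |
| 0.7 | 1.38 | 55% | 45% |
| 0.9 | 1.10 | 44% | 36% |
| one region only tested | – | 82% | 75% |

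A simulation of 4,000 replicates with a genotype covariate gave 59%, 45% and 36% at rho 0.5, 0.7 and 0.9 with 25 per cell, in agreement with the formula.

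**Step 4. Other effect patterns (interaction, 25 per cell).**
- d=1.06 in one region only: 43%, 60% and 86% at rho 0.3, 0.5 and 0.7.
- d=1.06 in seven of 11 regions, none in the rest: c = [7 − 49 rho/(1 + 10 rho)]/(1 − rho), which is 4.75 at rho 0.3. Power is 98% or more for rho 0.3 to 0.9.
- A linear fall from 1.06 to 0.53 across regions: 52%, 55% and 90% at rho 0.5, 0.7 and 0.9.

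**Step 5. Other contrasts (25 per cell, equal effect in all regions, rho 0.5 to 0.9).**
- Two cells, 25 against 25, d=0.74, noncentrality (n × d²/2) × c: 58% down to 35%.
- Marginal main effect, 50 against 50, d=0.74, noncentrality (n × d²) × c: 92% down to 68%.
- Two cells at the pilot d=1.3: 99% down to 89%.

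**Step 6. The region-by-region reading of Section 7.2.** The interaction at 25 per cell has 75% power in one region unadjusted. With Bonferroni over 11 (two-sided 0.05/11) it has about 40%.

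**The case against.** Nothing in Section 7.1 is miscalculated; both figures reproduce. Section 7.2 also promises a comparison in each region, and a one-outcome calculation is relevant to that. The low MANCOVA figures need two things the documents do not supply: a correlation of 0.5 or more, and the same effect everywhere. The background in Section 1.1.2 points away from a uniform effect. It reports the greatest binding in parietal and temporal cortices in AD, a hippocampal increase in MCI, and an entorhinal increase at follow-up.

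Most of this stands. A reader might infer that the study has only 36–60% power. The documents do not support that. The range holds for the interaction at 25 per cell under an assumed rho of 0.5 to 0.9 and a uniform effect, and it includes the drop from 30 to 25 per cell. At rho 0.3 the figure is 81%, and uneven effects can take it above 95%. A reader might also infer that the tests of diagnosis and amyloid status are equally weak. As marginal 50-against-50 comparisons at d=0.74 they keep 68–92% over the same rho range.

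The region-by-region reading does not rescue the 80%, as Step 6 shows. Nor does uneven binding: it makes the direction of the discrepancy unknown, and leaves the stated figure without a basis for this test.

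**Conclusion.** The point holds as a mismatch between the basis of the power statement and the named analysis. The 80% is a property of an unadjusted test on one region at 30 per group. It is not a property of the 11-region MANCOVA at 25 per cell, and this conclusion needs no assumption about correlation.

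The size and direction of the discrepancy cannot be fixed from the documents. Under the patterns examined, interaction power at 25 per cell runs from about 36% to above 95%. The possible shortfall concerns the interaction and two-cell contrasts at the minimal effect sizes. It does not extend to two-cell contrasts as large as the pilot d=1.3 when that effect is present in every region.

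The issue is distinct from the 30-versus-25 discrepancy. With a uniform effect and rho of 0.5 or more, MANCOVA power is below 80% even at 30 per cell (71% down to 44%).

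**What to change.** In Section 7.1, state that d=0.74 and d=1.06 are detectable effects for an unadjusted single-region contrast at 30 per group, and give the single-region interaction power at the 25 per cell of Section 7.2 as about 75%. Then either remove the implication of 80% power for the MANCOVA, or report MANCOVA power over a stated range of between-region correlations and effect patterns. A range is safer than one figure from a pilot covariance matrix. If the pilot is the 10 MCI patients and 13 controls described in Section 1.1.2 (an assumption), there are 21 within-group degrees of freedom for an 11-by-11 matrix, and its inverse may be unstable.

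In reporting, do not call a non-significant MANCOVA interaction an adequately powered null on the strength of Section 7.1.

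Making hippocampal SUVR the primary test so that it matches the power calculation is not recommended. Section 3.1.1 says PET imaging has ended, so this would be a late choice of endpoint, and it would narrow the objective in Section 2.1, which concerns spatial distribution. Any emphasis on a single region should be dated and disclosed relative to data access.

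The cost is a rewording and, if the second option is taken, one calculation. No subjects or procedures are added. The downside is that the stated power becomes less favourable.

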7.2 Statistical Methods

Subjects will be stratified using a two factor design based on diagnosis (impaired vs. normal) and amyloid status (positive vs. negative). Target sample size is 25 subjects per group (100 subjects total). ^{11}C -PBR28 binding will be the primary outcome measures. Between-group differences in SUVR values from ^{11}C -PBR28 PET images will be compared in each of the 11 ROIs. Analysis will be performed using a two-way MANCOVA with diagnosis (MCI vs. normal) and amyloid status (positive vs. negative) as independent variables and TSPO genotype status (high affinity vs. mixed affinity binder) as covariate. I will additionally test the interaction between diagnosis and amyloid status. This model will be fitted using PROC GLM in SAS.

Regression models will be fit for ^{11}C -PBR28 binding as dependent variable and cognitive scores, voxel count on MRI, ^{18}F -florbetaben binding, and CSF concentrations of markers of inflammation and neurodegeneration as independent variables.

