1.5 Dose Rationale and Risk/Benefits

Based on prior human experience and dosimetry data, we expect the proposed injected activity of ¹¹C-PBR28 (up to 20 mCi) to be safe without expected toxicity. ¹⁸F-florbetaben is an FDA-approved radiopharmaceutical used here for research purposes at injected activity recommended by the manufacturer (up to 8.1 mCi).

2 Study Objectives

2.1. The primary objective is to determine the extent and spatial distribution of inflammation at different stages along the cognitive spectrum of aging.

2.2. Secondary objectives are to determine how ¹¹C-PBR28 binding in brain relates to cognitive performance, amyloid binding, atrophy on MRI, and CSF concentrations of markers of inflammation and neurodegeneration.

3 Study Design

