3.2 Primary Study Endpoints

Because the drugs used in this study are radioligands given at tracer doses, there are no clinical endpoints of the study.

The primary outcome measures are:

1. Amount of ^{11}C -PBR28 binding in each of the four groups.

Secondary outcome measures are:

1. CSF concentration of inflammatory markers
2. CSF concentration of tau and phospho-tau

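### Section 7.2 plans no test of whether group effects differ between brain regions, although spatial distribution is part of the primary objective

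*Combined protocol and SAP*

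**What the plan says.** Section 2.1 gives a single primary objective: to "determine the extent and spatial distribution of inflammation at different stages along the cognitive spectrum of aging". Section 3.2 gives the primary outcome as the amount of "binding in each of the four groups", with no regional or pattern endpoint. Section 3.1.4 defines the regions: "Eleven ROIs will be extracted from the structural T1 image".

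Section 7.2 holds the whole primary analysis. Group differences in SUVR from "PET images will be compared in each of the 11 ROIs". The model is stated as: "Analysis will be performed using a two-way MANCOVA with diagnosis (MCI vs. normal) and amyloid status (positive vs. negative) as independent variables", with "TSPO genotype status (high affinity vs. mixed affinity binder) as covariate". One interaction is named: "I will additionally test the interaction between diagnosis and amyloid status". The fit is by PROC GLM.

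No section plans a region factor, a group-by-region term, a profile test or a contrast between ROIs. There is also no rule that the ROI comparisons follow only a significant omnibus test.

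**The concern.** A statement about spatial distribution compares regions: the group effect is larger here than there. Nothing in Section 7.2 tests that. The MANCOVA can be significant when binding is raised by the same amount everywhere. The ROI-by-ROI comparisons support a spatial claim only informally. If they are sorted into significant and non-significant regions, the sorting is not evidence that the effects differ. Correcting the 11 p-values for multiplicity would not supply the missing comparison.

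Regional contrasts carry weight in this protocol. Section 1.1.1 sets early amyloid in medial parietal and frontal cortex against early tau in medial temporal cortex. Section 1.1.2 draws an inference about neurodegeneration from a change in entorhinal cortex.

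**Working it through.** **1. Hypotheses.** Let β1,…,β11 be the adjusted group differences in the 11 ROIs.

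- MANCOVA omnibus test: H0 is β1 = … = β11 = 0 (11 constraints).
- Spatial question: H0 is β1 = … = β11, with no value specified (10 constraints).

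A uniform effect, βj = δ ≠ 0 for every j, violates the first hypothesis and satisfies the second. The first test therefore cannot answer the second question. The same holds for amyloid status and for the diagnosis-by-amyloid interaction.

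**2. The plan's own effect size.** Section 7.1 gives d=0.74 for 30 per group, 80% power and two-sided 5%. The normal approximation is (1.96+0.84)×√(2/30) = 0.72, and the noncentral t gives 0.736, so the figure reproduces. With the 25 per group of Section 7.2, two single groups have a detectable d of 0.81. The diagnosis main effect compares 50 with 50: 2.80×√(2/50) = 0.56, or 0.57 by noncentral t. The value 0.57 is derived here and is not stated in the plan.

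**3. Uniform effect, pattern read from unadjusted p-values.** Simulation: four cells of 25, 11 ROIs, and a model with diagnosis, amyloid, their interaction and genotype. The diagnosis effect d is identical in every ROI, and all ROIs have equal SD. The documents give no inter-ROI correlation, so ρ is an assumption. Share of simulated studies with 1 to 10 of the 11 ROIs significant for diagnosis:

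| d (50 vs 50) | ρ=0.5 | ρ=0.7 | ρ=0.85 |
|---|---|---|---|
| 0.57 | about 63% | about 50% | about 34% |
| 0.74 | about 25% | about 18% | about 14% |
| 1.3 | about 0% | about 0% | about 0% |

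**4. How the rates move.**

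- Holm adjustment of the 11 tests at d=0.57: 59%, 40% and 23%.
- ROI tests read only after a significant omnibus test: about 35%, 16% and 7% at d=0.57, and about 19%, 9% and 3% at d=0.74.
- A stricter definition of a pattern (3 to 8 ROIs significant) at d=0.74: about 6.5%, 6.4% and 4.8%.
- Pairwise comparison of two groups of 25 at d=0.74: 82%, 72%, 47%, 33% and 22% for ρ = 0.3, 0.5, 0.8, 0.9 and 0.95.

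**5. The region-by-diagnosis profile test.** With equal SDs it rejects at about its nominal 5% under a uniform effect. That depends on scale. Suppose, as an assumption, that ROI SDs range from 0.08 to 0.16 with d the same everywhere. At d=0.57 the raw difference is then 0.57×0.08 = 0.046 in one ROI and 0.57×0.16 = 0.091 in another. The raw-SUVR profile test rejects in about 25 to 34% of studies at d=0.57 and about 44 to 60% at d=0.74. It is right about raw change, but a reader could take the result as regional specificity when the standardised effect is uniform.

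**The case against.** The best defence is that the misreading is imputed. Section 7.2 never says that a region will be called affected or spared by its p-value. The objective can be read descriptively, and Section 3.2 names amount of binding with no regional contrast. Adjusted regional differences with confidence intervals, available from the same PROC GLM fit, would describe distribution without any test. This stands as a limit on the criticism. It does not fill the gap, because the plan does not commit to that descriptive approach either, and intervals for each ROI still do not compare regions.

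A reader might infer that the study's regional pattern will usually be spurious. The documents do not support that. The mixed-pattern rate depends on effect size, contrast and inter-ROI correlation. At the plan's d=0.74 for the diagnosis main effect it is about one in four or lower over the correlations in the table. It vanishes if the preliminary d=1.3 holds in every region, although Section 7.1 reports that value for the hippocampus only. An omnibus gate would lower the rates further, but the plan does not state one.

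It is also fair to object that a profile test on raw SUVR can create apparent regional differences when ROI SDs are unequal. This stands, and it shapes the fix.

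**Conclusion.** The concern holds as a gap between objective and analysis: spatial distribution is in the primary objective, and no planned test asks whether group effects differ between regions. That conclusion rests on the text alone and needs no simulation.

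The size is conditional. If regions are sorted by significance, a uniform diagnosis effect gives a mixed pattern in roughly a third to two thirds of studies at d=0.57, 14 to 25% at d=0.74, and almost none at a uniform d=1.3. These figures assume 25 per cell, equal SDs, one common correlation of 0.5 to 0.85, unadjusted tests and no omnibus gate. Pairwise group comparisons give higher rates.

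It would be wrong to conclude that the group comparisons are invalid. Inference on the extent of binding is not affected by this point. The plan should be changed, but the matter is not fatal to it.

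**What to change.** Keep the MANCOVA and add to Section 7.2:

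- **Test.** Region-by-diagnosis, region-by-amyloid and region-by-diagnosis-by-amyloid profile tests from the same PROC GLM model (REPEATED, or MANOVA with M= contrasts).
- **Scale.** State beforehand what counts as a uniform effect. One choice is SUVR standardised within each ROI to the pooled within-group SD or to the amyloid-negative unimpaired group, with raw and log SUVR as sensitivity analyses. The estimated SDs carry error that the standard profile test ignores. The relative standard error is about 1/√(2×24) = 14% from one group of 25, against 1/√(2×95) = 7% from the pooled residual (100 subjects less 5 parameters). The pooled SD is therefore preferable, with the p-value from a bootstrap that re-estimates the SDs in each resample.
- **Error rule.** For example, Holm across the three region terms.
- **Reporting.** Describe regions as differing only if the relevant term is significant, and then follow with a short pre-named set of between-region contrasts. The medial temporal versus medial parietal and frontal distinction in Section 1.1.1 is a natural candidate. Otherwise report ROI effects as estimates with confidence intervals. A non-significant region term should not be reported as proof of uniformity.
- **Timing.** Section 3.1.1 says that PET imaging has ended, so label the addition as made after imaging was complete.

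The cost is a short paragraph and a little more analysis on data already collected. The drawback is that fewer regional claims will be made.
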